2.2 Secondary Aims

R33 Phase: Assess the effect of HYCR on exercise capacity and quality of life.

Hypothesis 3: The improvement in exercise capacity, as measured by distance walked during the six min walk (6MW) test, in patients randomized to HYCR will be equivalent (not inferior) to patients randomized to CBCR.

Hypothesis 4: The improvement in exercise capacity, as measured by peak oxygen uptake (VO₂), in patients randomized to HYCR will be equivalent (not inferior) to patients randomized to CBCR.

Hypothesis 5: The improvement in quality of life (QOL), as measured by the Dartmouth COOP, in patients randomized to HYCR will be equivalent (not inferior) to patients randomized to CBCR.

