Advanced risk for falling will be assessed by the repetition 5X Sit-to-Stand test and cognitive status will be assessed by the Mini-Cog screening tool. Those patients meeting the exclusion criteria based in advanced risk for falling or cognitive status will be excluded from participating in the trial, but still allowed to participate in CR.

The Exercise Core Lab will oversee staff training, quality control, procedural conduct, and all data analysis for both the 6MW and CPX test. The primary modality for CPX testing will be the motor driven treadmill; however, a stationary bike can be used if indicated. Patients must use the same testing and exercises protocol for all CPX testing completed during the trial. For any bike tests, a ramped protocol will be used that starts at 0 watts and work rate is increased 10 watt/min. For all treadmill tests, the modified Naughton protocol will be used for testing:

Table 2.

Stage	1	2	3	4	5	6	7	8	9	10
Time (min)	2	4	6	8	10	12	14	16	18	20
Speed (mph)	1.0	1.5	2.0	2.0	2.0	3.0	3.0	3.0	3.0	3.5
Grade (%)	0	0	3.5	7	10.5	7	10	12.5	15	14
Estimated METs	2.3	3.3	4.5	5.5	6.5	7.5	8.5	9.5.	10.5	11.5

Patients will be excluded from the study if exercise testing results preclude safe exercise training in CR as defined by ACC/AHA guidelines, including abnormal blood pressure response, early ischemic changes and unexpected life-threatening arrhythmia. If an exercise-induced arrhythmia is identified as life-threatening, the exercise test will be stopped. If the patient is performing a baseline exercise test, he/she will not be randomized in to the study. If the patient is performing a follow-up exercise test immediately after CR or at 6 month, he/she will be asked to stop any exercise training and his/her physician will be notified of the results; these patients will be followed per protocol for the duration of the study and no further exercise testing will be performed. Patients who have a non-life-threatening arrhythmia that stops the test can re-take the test or re-start CR after it is treated.

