4.6. Retention

Retention for iATTEND is defined as compliance with scheduled testing sessions (baseline and follow-up visits 1 and 2), as well as compliance with scheduled follow-up telephone calls with the study coordinator (at months 2 and 4 after completing CR). A main reason for the telephone calls at months 2 and 4 of follow-up is to facilitate continued subject retention/engagement in the trial. The coordinator will remind patients about their scheduled follow-up visit 2 (at 6 months). Also, the coordinator will equally speak with subjects in both groups about any barriers/issues they might be experiencing relative to proper self-care or disease management behaviors, and assist with resolution strategies using an open, problem-solving approach. Subjects that are administratively “dropped” from CR will still be contacted and scheduled to complete follow-up testing visits 1 and 2.

Relying on data provided by the SRRSA, the PMT will regularly review reports detailing subject retention to follow-up testing and telephone calls and in conjunction with the Steering Committee, enact measures (telephone calls by research and clinical staff, email, and U.S. mailed letters) to help ensure fidelity to the specified protocol for testing. Project budgeted gas cards (\$10 each) can be provided to help defray subjects’ travel costs associated with baseline testing and follow-up visit 1 and 2 testing.

The SRRSA sub-committee will (a) track and report on project issues that impact patient retention to the above testing events and follow-up telephone calls, as well as (b) staff compliance to protocol procedures. The later includes the SRRSA committee periodically (every 6 months) conducting shadow-evaluations (using video and observation) of CR staff for the uniform conduct of patient assessments and the uniform delivery of CR per protocol standards.

4.7 Drop outs.

4.7.1. *Drop out recovery.*

Relative to study retention, the following definitions will be applied:

1. *Integrated* subjects are those attending all appointments as scheduled, or rescheduling any missed appointments or cancellations
2. *Poorly compliant* subjects are those who cancel, do not show and fail to reschedule 2 of their 4 follow-up responsibilities (follow-up visit 1 or 2 and telephone encounter 1 and 2).
3. *Refusals/drop-outs* are those that state, in no uncertain terms, that they do not want to participate any longer in the trial, and refuse any further contact with study staff.

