iATTEND will use a systematic approach in an attempt to recover poorly compliant subjects, especially those that either (a) inquired about or expressed interest in dropping or (b) or appear to be “moving toward” dropping out based on poor compliance data. Since most drop outs are due to life changes (e.g., divorce, illness of family member, change in jobs) and/or misunderstandings with research staff, a planned recovery approach will be used that addresses the following.

1. Be sure that subjects are NOT pushed to the point that they refuse to participate/all contact
2. Stay in touch with the patient though email, phone calls or being present at planned clinic visits they may have with their physicians. All of this is aimed at showing support, as well as provides an opportunity to garner subject concerns such that problem solving and barrier resolution techniques can be applied to prove participation.
3. To foster continued, planned contact with the research staff... even if it is something as simple as to schedule another contact on a specific day and time.

Engaging patients at risk for dropping out using barrier identification and problem resolution techniques is a dynamic endeavor that also can vary with time, especially among those subjects where challenging life circumstances (e.g., transportation, work, family care) change improve... such that it then becomes more feasible for them to re-engage in the project.

4.7.2. *Other important drop out recovery considerations.*

- A. Attempts to re-integrate a participant should be discontinued as soon as an adamant refusal is communicated.

B. A patient will be considered “lost to follow-up” only after all means of contact have failed. The status of the patient at the last visit or contact will be used for the final analysis. The vital status of these patients will be followed by appropriate national database.

C. For patients that formally withdraw consent, vital status will be followed by appropriate national database.

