10.1. Randomization Procedure

Using computer generated randomization, the randomization process will be stratified by race and sex and blocked to ensure balance at random accrual points. Lists were compiled for the 4 sex-race specific strata. As new participants are added to the study they will be assigned the next available treatment assignment (CBCR, HYCR) based on the lists provided. The project manager will be responsible for treatment assignment as all other staff involved in the study will be blinded as to the randomization lists to avoid bias.

10.2. Sample size and power calculations.

We propose to enroll a total of 270 patients evenly randomized into two groups of 135 patients each. To determine power for **Hypothesis 1**, we will use a Student's t-test approach. From recent data from our administrative CR data base, we believe that the CBCR group will complete 21 ± 13 (mean + sd) visits over the course of the study. The test, with a two-sided 0.05 alpha level, will have 80% power to detect an increase of 4.5 visits. We believe this to be a clinically significant difference (5).

Also, for **Hypothesis 2**, our recent administrative data indicates that 24% of patients in our CBCR program complete 36 visits. A chi-squared test with a two-sided 0.05 alpha rate and 135 subjects per group will have 80% power to detect an **increase to 39.8% or more in the HYCR group** (effect size=15.8 percentage point increase).

Hypothesis 3, 4 and 5 require longitudinal measures six months after CR is completed, so it is possible that some lost to follow-up will occur at follow-up testing point number 2. If we assume that no more than 20% will be lost, our sample size for this analysis will be at least 108. We anticipate a standard deviation of the change in meters walked in the 6-minute walk to be 107 meters (based on data from the Henry Ford Core Exercise Laboratory) When the sample size in each group is 108, a two group 0.05 one-sided t-test will have in excess of 90% power to reject the null hypothesis that the CBCR and HYCR groups are not equivalent (the difference in means is 50 meters or farther), in favor of the alternative hypothesis that the means in the two groups are equivalent.

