The measured of peak VO₂ should have a standard deviation near 6 (86). With a sample size of 108 per group, a two-group one-sided t-test will have greater than 80% power to reject the null hypothesis that the CBCR and HYCR groups are not equivalent (the difference in means is 2.0 mL/kg/min or farther), in favor of the alternative hypothesis that the means in the two groups are equivalent.

Based on Campbell, et al. (87), we anticipate that the standard deviation of the Short Form Health Survey (SF-12) physical component summary will be 22 and the mental component summary will be 18. When the sample size in each group is 108, a two-group 0.05 one-sided t-test of the physical component scale will have 80% power to reject the null hypothesis that the

CBCR and HYCR are not equivalent (the difference in means is 7.5 or further from zero in the same direction), in favor of the alternative hypothesis that the means of the two groups are equivalent. The power for the mental component summary will exceed 90%.

10.3. Data Analysis Plan.

Data analysis will begin with preparatory activities such as checking for complete data entry, identification of outliers, and other such data cleaning tasks. Once the above tasks are completed, the data base will be “locked” for analyses. The Statistical Analysis System, (SAS, version 9.4) will be used for data analysis. A detailed descriptive analysis of all quantitative data will be performed involving the summarization of data and the use of inferential and graphical exploratory analytic techniques. The information obtained from this preliminary investigation will be used to: 1) describe univariate and bivariate sample distributions of the data; 2) identify the interrelationships between variables (i.e., need for covariate adjustment); and 3) check for violations of assumptions underlying identified statistical techniques (e.g. independence, linearity, homoscedasticity, normality). In the event that statistical assumptions are severely violated, data transformations or nonparametric methods will be employed. An intention to treat approach will be utilized for all analyses. For hypothesis 1 the number of visits completed before lost to follow up will be used and for hypothesis 2 a yes/no response will be generated based on the observed data.

R33- Primary Aim: Assess the effect of a HYCR program on over-all patient attendance

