For the **Primary Hypothesis** (number of sessions completed), if the distribution of the number of sessions completed is normal then a Student’s t-test will be used for comparison of the two groups. In the likely event it is skewed a two-sample Wilcoxon with a Fligner-Policello correction for unequal variances will be used. **Hypothesis 2** (percentage of patients completing 36 CR sessions) will be addressed using a Chi-squared test for comparison of proportions.

R33- Secondary Aim: Assess the effect of HYCR on exercise capacity and quality of life.

Hypotheses 3 and 4 (both address measures of exercise capacity) and **Hypothesis 5** (QOL) all involve assessing if the two group responses are equivalent. A two one-sided test approach will be used to demonstrate equivalence between the two groups.

There are several identified **exploratory aims** for this project, including but not limited to:

- (a) short-term (6 month) retention of CR-related outcomes [e.g., exercise capacity, QOL, and self-engaged (not CR) purposeful exercise and total physical activity habits]
- (b) program cost effectiveness.

Analyses of the exploratory aim associated with the short-term retention of CR-related outcomes will be analogous to the analyses described above, such that Student's t-test, Chi-squared tests or their nonparametric alternatives will be utilized.

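### Hypotheses 3 to 5: the two-group equivalence test has no baseline, race or sex term (valid, but less precise), and the plan has no agreed rule for lost patients

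*Combined protocol and SAP*

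**What the plan says.** **Comparison and model.** Section 2.2 words the secondary hypotheses as improvement; Hypothesis 3, for example, concerns "The improvement in exercise capacity, as measured by distance walked during the six min walk (6MW) test". Section 5.2 lists change upon completion of CR. For all three hypotheses section 10.3 states: "A two one-sided test approach will be used to demonstrate equivalence between the two groups". It names no covariate. Sections 4.3.4 and 10.1 stratify randomization by race and sex. Section 10.3 leaves the question of covariate adjustment to a descriptive look at the data after database lock and does not say that this look is blinded. Under section 7.3 the biostatistician who runs the analyses holds the randomization codes.

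**Lost patients.**
- Section 10.3: "An intention to treat approach will be utilized for all analyses". The rule that follows covers two hypotheses only: "For hypothesis 1 the number of visits completed before lost to follow up will be used and for hypothesis 2 a yes/no response".
- Section 10.2, for Hypotheses 3 to 5, after allowing up to 20% loss at follow-up visit 2: "our sample size for this analysis will be at least 108".
- Section 4.7.2, on patients lost to follow-up, with no endpoint named: "The status of the patient at the last visit or contact will be used for the final analysis".
- Section 4.6: patients administratively dropped from CR "will still be contacted and scheduled to complete follow-up testing visits 1 and 2".
- Section 4.3.3.c: after a life-threatening arrhythmia on a follow-up exercise test, "no further exercise testing will be performed".

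**Time point.** Section 10.2 ties Hypotheses 3 to 5 to six months after CR. Section 5.2 lists the end of CR as secondary and six months as exploratory.

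**The concern.** There are two separate matters. First, the trial measures each outcome at baseline and stratifies by race and sex, yet the named test uses none of this. Omitting prognostic covariates from a randomized comparison does not make it invalid, but the confidence interval is wider than it need be. An equivalence claim depends on that width. Leaving the choice of covariates until after lock also leaves the analyst a discretion that serves no purpose.

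Second, the sections allow at least two different analyses of the same data: observed cases (about 108 per group), or all 135 with the last value carried. In an equivalence test the choice matters more than usual. Filling gaps with no change can pull the arms together and so favour the hypothesis. Intention to treat is therefore not automatically the cautious option, and the rule should be fixed before anyone sees results.

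**Working it through.** **Inputs from section 10.2.** 135 per group; 135 × (1 − 0.20) = 108. One-sided alpha 0.05. Six-minute walk: SD of change 107 m, margin 50 m. Peak VO2: SD 6, not said to be of level or change; margin 2.0 mL/kg/min. **Assumptions.** The baseline/follow-up correlation r and every loss rate before visit 1, because the documents give none.

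**1. The plan's own figure.** Two one-sided tests (TOST), true difference zero: power = 2Φ(margin/SE − 1.645) − 1, with SE = SD × √(2/108).
- Walk: SE = 107 × 0.1361 = 14.56 m; 50/14.56 − 1.645 = 1.789; Φ = 0.963; power = 0.926 (0.925 with the t distribution). The stated figure of over 90% is reproduced.
- Peak VO2: SE = 6 × 0.1361 = 0.8165; 2.0/0.8165 − 1.645 = 0.804; Φ = 0.789; TOST power = 0.579 (0.574 with t).

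**2. Adding the baseline value.** With equal variances at both visits:
- If the SD is of change, the ANCOVA SD is SD × √((1 + r)/2). The variance ratio is 0.75/0.85/0.95 at r = 0.5/0.7/0.9, so 108 per group act like 144/127/114.
- If the SD s is cross-sectional, the change-score SD is s√(2(1 − r)) and the ANCOVA SD is s√(1 − r²).

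TOST power, unadjusted to ANCOVA:

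| Endpoint, reading of SD | r = 0.5 | r = 0.7 | r = 0.9 |
|---|---|---|---|
| Walk, SD of change 107 | 92.5 to 97.9% | 92.5 to 96.1% | 92.5 to 93.8% |
| Peak VO2, SD of change 6 | 57.4 to 76.0% | 57.4 to 68.4% | 57.4 to 61.0% |
| Peak VO2, cross-sectional SD 6 | 57.4 to 76.0% | 86.8 to 92.4% | about 100% for both |

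In 20,000 simulated trials with arm, baseline, race and sex in the model, the walk gave 97.8/95.8/93.5%. With a true peak VO2 deficit of 2.0 and r = 0.7, the error rate was 4.7% unadjusted and 4.9% adjusted, so both tests hold their level. No figure is given for Hypothesis 5: it names the Dartmouth COOP, while section 10.2 gives an SD and margin only for the SF-12.

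**3. Last status read as zero change.** Put the true deficit at the margin, assume equal loss L in each arm, and let lost patients otherwise show the full arm difference. The observed deficit becomes (1 − L) × margin, with 135 per group. Take the CBCR gain equal to the margin and the HYCR gain as zero.
- Walk, L = 0.20: deficit 40 m. Variances: CBCR 0.8 × 107² + 0.16 × 50² = 9,559; HYCR 0.8 × 107² = 9,159. SE = √(18,718/135) = 11.8 m. Φ((50 − 40)/11.8 − 1.645) = 0.21.
- L = 5/10/20%: walk 7/11/21%; peak VO2 7/9/15% (SD of change 6). Nominal is 5%.

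**4. Other assumptions, walk.**
- Zero change, unequal loss, CBCR gain 50 or 75 m: 5 to 7% with CBCR 5% and HYCR 15% lost; 15 to 20% with these reversed.
- Observed cases, loss unrelated to outcome: 5%. Lost HYCR patients worse than HYCR completers by the margin: 7/10/17% at L = 5/10/20%.
- Lost patients with no arm difference, overall deficit 50 m, L = 0.20: completer deficit 50/0.8 = 62.5 m. Zero change gives 5.0% and observed cases 0.6%, so the ranking reverses.
- Visit 1 carried to visit 2, L = 0.20, visit-2 deficit 50 m: a visit-1 deficit of 0/50/75 m gives an analysed deficit of 40/50/55 m and false equivalence of 19/5/2%.

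**5. Does the adjusted model cure informative loss?** No. Take 20% loss with lost HYCR patients worse by the margin and baseline not predicting loss. ANCOVA gives 19.6/18.3/17.3% at r = 0.5/0.7/0.9, against 16.8% unadjusted.

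**The case against.** **Adjustment.** It can be called a preference. The unadjusted test is valid, the walk already has 92% power, and section 7.1 has the Steering Committee approve a main analysis plan in which covariates could be named. The source cited for the SD of 6 is titled as a study of aerobic capacity at entry to CR, which suggests a cross-sectional SD and a smaller gain. The low peak VO2 base also reflects powering a single one-sided test (79% by the same arithmetic) instead of the TOST, which is a separate matter. All of this stands as a limit on size. None of it is a reason to forgo a free gain, and the documents contain no such named covariates.

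**Loss rule.** The 108 is a power figure, not a declared analysis set. The sentence after the one in section 4.7.2 concerns vital status, so status there may not mean outcome values. The 20% belongs to visit 2. These points stand: carrying last status into Hypotheses 3 to 5 is one reading, not a stated plan. The silence of section 10.3 on these hypotheses remains.

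**Arrhythmia rule.** A reader might infer that it leaves all three outcomes missing. Section 4.3.3.b puts the walk and the quality-of-life forms before the CPX test at each visit. The point is therefore limited to peak VO2 and to visit 2 testing.

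**Conclusion.** The point holds in two parts, both about secondary hypotheses.

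1. The planned test is valid but less precise than it could be at no cost. The gain is 1 to 5 percentage points of power for the walk. For peak VO2 it runs from nothing to 19 points, depending on an unstated correlation and on which SD the 6 is.
2. The documents do not settle how lost patients enter Hypotheses 3 to 5. The error rates above show that the choice can matter; they are not a forecast of this trial.

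Three stronger readings are tempting and unsupported:
- That omitting covariates inflates the error rate. It does not.
- That the plan carries last values forward and so has a 21% false-equivalence rate. No section says this for these endpoints; that figure needs zero change, 20% loss before visit 1 and the full arm difference in lost patients.
- That covariates will be chosen after treatment results are seen. The documents do not say so; they only fail to rule it out.

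Confidence is medium, because r and early loss are assumed throughout.

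**What to change.** 1. For Hypotheses 3 to 5, pre-specify ANCOVA, or a likelihood-based repeated-measures model, with arm, baseline value, race and sex. Take equivalence from its 90% confidence interval. Name these covariates before unblinding, in place of data-driven selection.
2. State that last status is not carried forward for these endpoints, and reconcile sections 4.7.2, 10.2 and 10.3. Say how peak VO2 and visit 2 values missing under the arrhythmia rule enter the analysis.
3. Reconcile the time point between sections 5.2 and 10.2, since it decides which losses matter.
4. Handle losses by the model or by multiple imputation. Because both assume data missing at random, add one sensitivity analysis unfavourable to equivalence, for example lost HYCR patients imputed worse by the margin.

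Leave the planned tests for Hypotheses 1 and 2 as they are. The cost is SAP wording, a few lines of code and a model to explain, using data already collected. If r is near 0.9 the precision gain is small (at most about 4 points for the walk and peak VO2), but items 2 to 4 are worth having whatever r is.

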Appendix A

DATA SAFETY MONITORING PLAN

The data safety monitoring plan will adhere to all policies and procedures set forth by Henry Ford Hospital, its Office of Research Administration, and its Institutional Review Board (IRB). Additionally, all defined unexpected adverse events and unanticipated problems will be reported to the system's IRB, data safety monitoring board (DSMB), and other applicable regulatory agencies.

To help ensure subject safety, the following procedures will be followed:

- a) Based on review of the System's EMR and/or in-person interview/examination with study staff, potential subjects will be carefully "screened-out" during the trial's screening processes for known contraindications to exercise testing and exercise training (e.g., receiving continuous inotropic support therapy).
- b) All study-eligible subjects will complete a symptom-limited graded cardiopulmonary exercise (CPX) test at baseline, prior to randomization. This test has the ability to identify and screen patients for rare exercise-induced contraindications to exercise training (e.g., abnormal blood pressure response, significant dysrhythmia).

Concerning home-based CR, it is important to emphasize that most all patients that participate in center-based programs today are already asked to "exercise on their own on non-rehab days"; therefore, this study is mainly giving some structure and supervision to that recommendation.

- c) All subjects will also attend at least one exercise session in center based CR, during which their gait, balance and stability on their preferred exercise modality will be evaluated to ensure the patient will be safely able to use the equipment on their own.
- d) Published guidelines for prescribing exercise in the CR setting will be followed, such as progressing exercise duration and frequency before intensity, reinforcing proper warm-up and cool down procedures, the periodic screening for exercise-related signs or symptoms, and progressing and maintaining exercise training intensity to stay within prescribed levels based on heart rate or rating of perceived exertion.
- e) At the beginning of each remote telemedicine CR session, we will document the patient's exact current street address/location (e.g. home, community fitness center, workplace), for the rare instance that an untoward event occurs that requires intervention by emergency medical services.

The Data Safety Monitoring Board (DSMB). For this trial the DSMB will be an "internal DSMB", comprised of 4 individuals that are independent of the NHLBI, trial investigators, and trial management. The NHLBI will approve the membership of the DSMB and the DSMB is advisory to the NHLBI and the trial's Steering Committee.

The primary endpoint for this study is number of sessions attended (not a clinical outcome such as mortality). However, trial safety is always a concern. Therefore, rare, untoward, unexpected major events related to exercise training or exercise testing (i.e., during or within three hours) may occur and will be monitored, such as death or events requiring hospitalization (e.g., myocardial infarction, syncope, arrhythmia, fall). These events will be reported to both the IRB and DSMB per existing institutional and protocol requirements (i.e., within 10 days) and documented in the subject's study file.

Monitoring of events. A DSMB meeting will be held in-person (with teleconference capabilities) every six months, during which a comparison will be made of any excess, untoward events. If needed, the DSMB will advise the NHLBI and Steering Committee accordingly. Minor events, such as falls not requiring emergency care, angina, and ST segment changes during testing that are suggestive of myocardial ischemia will be documented in the subject's study file.

Relative to suspending or discontinuing a specific subject's participation in CR and/or the trial assessments due to a clinical indication (worsening symptoms, compromising arrhythmia), [name] will consult with co-investigators Drs. [name] or [name] to ensure that all applicable and relevant Henry Ford Hospital and Preventive Cardiology Unit program- and patient-level clinical policies and procedures are followed. With the subject's permission, and to assist with their care, their own physician will be contacted regarding the relevant clinical findings. The Steering Committee will be informed of the above.

Since a clinical endpoint such as death or re-hospitalization does not represent a trial endpoint or outcome measure for this project, the DSMB will not have to address the issue of trial continuation relative to endpoint futility. All subjects will be evaluated for the specified duration of the trial for all primary and secondary outcomes measures. The number of subjects that withdraw consent from trial participation will be tracked and reported.

The monitoring for unexpected major adverse events and minor events, as well as patient withdrawals, will occur continuously through the study by the project manager and research coordinator. Major events will be discussed within the project management team.

It will be the responsibility of the study coordinator, in conjunction with [name], to ensure that unexpected serious/major adverse events that occur within 3 hours of exercise are collected, summarized and reported within 10 days to the local IRB and to the DSMB. Although the occurrence of an unexpected, major adverse events is not anticipated and felt to be extremely rare, any such events that do occur will be investigated and discussed jointly between the principal investigator and the DSMB or its chair. Any policy or procedural changes that arise from such discussion will be incorporated into a revised study protocol. Subjects that withdraw consent from trial participation will also be tracked by the study coordinator and reported to the DSMB.
